11.2.2.2 Missing Data

Missing data will be reported descriptively. In general, imputations of missing observations will not be made. Any additional sensitivity analysis concerning missingness and details regarding handling of missing data will be described in the statistical analysis plan (SAP).

Continued collection of efficacy data for patients who discontinue treatment will be made as far as possible.

11.2.2.3 Demographic and Baseline Characteristics

For Cohort 1, descriptive summaries of demographics and other baseline characteristics (including medical and surgical history) will be presented overall using the FAS. For Cohort 2, descriptive summaries of demographics and other baseline characteristics will be presented overall for the full analysis set as well as by the underlying diagnostics subgroups.

Prior medication will be summarized overall using the full analysis set.

11.2.2.4 Subject Disposition

The following will be summarized overall by Cohort:

- Patients enrolled (who signed the informed consent)
- Patients treated
- Patients completing treatment
- Patients discontinuing treatment and reason
- Patients completing the study
- Patients withdrawing early (including withdrawal reason)

Additionally, patients enrolled, included in the FAS will be summarized by region by Cohort.

11.2.2.5 Evaluation of Primary Efficacy Variables

The proportion of positive pruritus assessments at the patient level over the 72-week treatment period will be summarized. A positive pruritus assessment is defined as a scratching score of ≤ 1 or at least a one-point drop from baseline on the Albireo ObsRO instrument. At each assessment, the AM score will be compared to the baseline AM average, and the PM score will be compared to the baseline PM average. Both AM and PM pruritus assessments will be included in the analysis of this endpoint. Baseline will be defined as the average score from 14 days prior to treatment start in Study A4250-008 for AM and PM, respectively.

Fasting serum bile acids baseline will be calculated as the average of the pre-dose value in Study A4250-008 (Visit 1) and the previous visit (Visit 8 in study A4250-005) for Cohort 1. Fasting serum bile acids baseline will be calculated as the average of Visit S-2 and the pre-dose Visit 1 values in Study A4250-008 for Cohort 2. The end value is the average of the values at Weeks 70 and 72 in study A4250-008.

The change from baseline over the Treatment Period in serum bile acids will be analyzed mainly by using descriptive statistics. Change over time will also be displayed using graphical presentations (e.g., a spaghetti plot which illustrates the change in both Study A4250-005 and Study A4250-008 by treatment group in Study A4250-005). In addition, change from baseline 1 to end of treatment will be analyzed by using one-sample T-test or Wilcoxon signed-rank test as appropriate.

As an exploratory analysis of pruritus and serum bile acids, a comparison of treatment with A4250 120 $\mu\text{g}/\text{kg}/\text{day}$ during the first 24 weeks of Study 008 vs placebo patients over the 24-week treatment period from Study 005 will be carried out.

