6 STUDY OBJECTIVES

6.1 Primary Objectives

Primary Objective (Cohort 1)

To demonstrate a sustained effect of A4250 on serum bile acids and pruritus in children with PFIC Types 1 and 2.

Primary Objective (Cohort 2)

To evaluate the effect of A4250 on serum bile acids and pruritus in patients with PFIC who either (1) do not meet eligibility criteria for Study A4250-005 (PEDFIC 1) or (2) who do meet the eligibility criteria for Study A4250-005 after recruitment of Study A4250-005 has been completed.

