9.1.3 Exploratory Efficacy Endpoints

All Exploratory Endpoints will be evaluated at Weeks 24, 48, and 72 unless otherwise noted. Baseline is calculated prior to initiation of A4250 treatment. Exploratory endpoints include:

- Change in serum ALT, GGT, and total bilirubin concentration from baseline to Week 72
- Proportion of individual assessments meeting the definition of a positive pruritus assessment at the patient level over the 72-week Treatment Period. A positive pruritus assessment includes an itch score ≤ 1 , or at least a one-point drop from baseline based on the Albireo PRO instrument; only patients ≥ 8 years of age will complete the Albireo PRO instrument
- Change from baseline over the 72-week treatment period in sleep parameters measured with the Albireo PRO and ObsRO instruments
- Change from baseline in INR, albumin, liver enzymes, leukocytes, and platelets
- Change from baseline measures of bile acid synthesis (autotaxin, p-C4)
- Assessment of Global Symptom Relief at Weeks 4, 12, 24, 48, and 72 as measured by patient, caregiver, and clinician PGIC items
- Change from baseline by each 4-week interval between Visit 1/Screening and Visit 5/Week 24, then by each visit between Visit 5/Week 24 to Visit 12/Week 76 in patient-reported and observer-reported night time itching and scratching severity scores, respectively
- Change from baseline by each 4-week interval between Visit 1/Screening and Visit 5/Week 24, then by each visit between Visit 5/Week 24 to Visit 12/Week 76 in patient-reported and observer-reported morning time itching and scratching severity scores, respectively
- Change from baseline by each 4-week interval between Visit 1/Screening and Visit 5/Week 24, then by each visit between Visit 5/Week 24 to Visit 12/Week 76 in pooled pruritus score including observer-reported scratching for patients < 8 years of age and patient-reported itch severity for patients ≥ 8 years of age

- Change from baseline by each 4-week interval between Visit 1/Screening and Visit 5/Week 24, then by each visit between Visit 5/Week 24 to Visit 12/Week 76 in additional patient-reported and observer-reported sleep parameters (e.g., tiredness, number of awakenings)
- Change from baseline in PedsQL questionnaire
- Change from baseline in stage of liver fibrosis as assessed by Fibroscan® (where available)
- Change from baseline in stage of liver fibrosis as assessed by post-treatment biopsy (when available)

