9.2.2 Itching and Sleep Score

Itching, observed scratching, and sleep disturbance will be assessed twice each day via eDiary. Patient/caregivers will be instructed to fill in the eDiary every morning and evening for the first 24 weeks and the last 21 days before all the remaining visits to the clinic. There will be no interruption between Visits 11 and 12. Patients and/or caregivers will be instructed to complete the eDiary in the morning after the patient wakes and in the evening just before the patient goes to sleep.

The eDiary includes Albireo ObsRO and PRO items. Patients <8 years of age will not be asked to complete the Albireo PRO items; only the Albireo ObsRO will be completed by caregivers of patients in this age group. Older patients, ≥ 8 years of age, will complete the Albireo PRO items and the caregiver will complete the Albireo ObsRO items. The Albireo PRO items assess severity of itch, aspects of sleep disturbance (morning diary only), and tiredness. For patients 8 to 12 years of age, the caregiver will read the Albireo PRO items along with the child and record the child's response. A guide will be provided to the caregivers that provides standardized explanations of the Albireo PRO items, in case the patient is confused or requires clarification about the meaning of a question. The Albireo ObsRO items assess severity of observed scratching, aspects of observed sleep disturbance (morning diary only), and observed signs of tiredness (evening diary only). The Albireo ObsRO and PRO scratching and itch severity items use 0 to 4 response scales, where each response is distinguished by a unique facial expression, verbal anchor, number, and color code ([Appendix 2](#)).

A daily score AM and PM for the Albireo ObsRO scratching item will be averaged from the 2 ratings for each day. A daily score will be considered missing if both of the daily assessments are missing. A weekly score will be calculated by averaging the daily scratching scores. A weekly score will be considered missing if ≥ 4 out of 7 days a week of data are missing. For AM and PM baseline, a 14-day daily score of AM and PM prior to the first dose of study medication will be averaged as the baseline score.

For AM baseline, a 14-day AM score prior to the first dose of study medication will be averaged as the baseline AM score. The same approach will be used for PM baseline and to calculate a patient-reported itch severity score.

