11.2.2 Methods of Statistical Analyses

11.2.2.1 General Principles

Descriptive statistics will mainly be used in this open-label extension study. Patients with BRIC will be presented separately in efficacy assessments. All statistical analyses will be performed using SAS version 9.3 or higher.

Baseline 1 will be defined as the last value prior to treatment start in Study A4250-005 for Cohort 1 patients.

Baseline 2 will be defined as the last value prior to treatment start in Study A4250-008 for all patients. Baseline 2 will be used in all analyses unless otherwise specified.

Descriptive statistics will be summarized for Cohort 1, Cohort 2 excluding BRIC, Cohort 2 BRIC, and combined Cohort 1 + Cohort 2 excluding BRIC. Within Cohort 1, the following subgroups will be presented: ‘A4250 40 µg/kg/day (-005) to 120 µg/kg/day (-008)’, ‘A4250 120 µg/kg/day (-005) to 120 µg/kg/day (-008)’, ‘A4250 40 µg/kg/day (-005) and 120 µg/kg/day (-005) to 120 µg/kg/day (-008)’, and ‘placebo (-005) to 120 µg/kg/day (-008)’. Within Cohort 2 excluding BRIC, 3 subgroups (‘40 µg/kg/day’, ‘40 µg/kg/day to 120 µg/kg/day’, and ‘120 µg/kg/day’) will be presented. Cohort 1 Placebo to A4250 120 µg/kg/day will also be combined with Cohort 2 excluding BRIC for presentations.

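### For Cohort 1 children already on A4250 in Study 005, the one-point-drop part of the pruritus endpoint starts from an on-treatment baseline and scores sustained partial responses as negative

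*Protocol*

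**What the plan says.** The Cohort 1 primary objective (section 6.1) is "To demonstrate a sustained effect of A4250 on serum bile acids and pruritus in children with PFIC Types 1 and 2". The US primary endpoint, which is secondary elsewhere, is each patient's proportion of positive pruritus assessments over 72 weeks (sections 9.1.1 and 9.1.2).

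Section 11.2.2.5 calls an assessment positive if it shows a "scratching score of ≤ 1 or at least a one-point drop from baseline on the Albireo ObsRO instrument". The comparison is made score by score: "At each assessment, the AM score will be compared to the baseline AM average", and PM likewise. The reference is fixed: "Baseline will be defined as the average score from 14 days prior to treatment start in Study A4250-008 for AM and PM, respectively".

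Section 11.2.2.1 defines Baseline 1 (before 005 treatment, Cohort 1) and Baseline 2 (before 008 treatment, all patients), and adds: "Baseline 2 will be used in all analyses unless otherwise specified". The only Baseline 1 analysis in section 11.2.2.5, a one-sample test of change to end of treatment, stands in the serum bile acid paragraph. Section 9.1.3 says of the exploratory endpoints: "Baseline is calculated prior to initiation of A4250 treatment". Section 11.2.2.1 also calls for a combined summary of Cohort 1 with Cohort 2 excluding BRIC.

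**The concern.** Section 7.1.1 makes Visit 1 of 008 the same visit as Visit 9 of 005, and Appendix 7 labels it the 005 end-of-treatment visit. For children who took 40 or 120 µg/kg/day in 005, the 14 baseline days are therefore their last days on that treatment. From there, a one-point drop records additional benefit during 008. A child whose scratching eased partly in 005 and stayed eased has exactly the outcome the objective describes, yet can score no positive assessments.

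At stake is a regional primary endpoint that under-counts maintained benefit in the patients for whom maintenance is the question. In addition, the combined-cohort summary averages changes from on-drug and drug-free baselines, so its value depends partly on how many prior-active patients are in the pool.

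**Working it through.** **Inputs.** The response rule and baseline are from section 11.2.2.5. Section 9.2.2 says the "scratching and itch severity items use 0 to 4 response scales", and Appendix 2 shows whole-number answers. The 005 arms (40, 120 µg/kg/day, placebo; 24 weeks) are in section 5.2.2. Write B1 for the 14-day average before the first 005 dose and B2 for the 14-day average before the first 008 dose.

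The protocol gives no pruritus figure to reproduce. Its one power statement (section 11.1) concerns diversion, transplantation or death. An exact binomial calculation gives 89.8% at n=48 and 96.6% at n=60, in line with the stated 89% to 96%. It has no bearing on this point.

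**Step 1: when the drop part adds anything.** A score s above 1 is positive only if baseline − s ≥ 1, that is, baseline ≥ s + 1. Score 2 needs a baseline of at least 3; score 3 needs 4; score 4 would need 5, which is impossible. Below a baseline average of 3, the drop part adds nothing to the ≤1 part.

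**Step 2: when B1 and B2 disagree.** Taking B2 no higher than B1, they disagree only for scores of 2 (B1 ≥ 3, B2 < 3) and scores of 3 (B1 = 4, B2 < 4). If B1 is below 3, every assessment is classified identically.

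**Step 3: a perfectly sustained response**, with the on-treatment score equal to B2 and unchanged to Week 72:

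| B1 | Held score | Against B1 | Against B2 |
|---|---|---|---|
| 3 | 1 | positive (≤1) | positive (≤1) |
| 2.5 | 2 | negative (drop 0.5) | negative (drop 0) |
| 3 | 2 | positive (drop 1) | negative (drop 0) |
| 4 | 2 | positive (drop 2) | negative (drop 0) |
| 4 | 3 | positive (drop 1) | negative (drop 0) |

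**Step 4: with day-to-day variation.** Assume stable scores with mean m and SD 0.7 before rounding, 3 ≤ B1 < 4 and B2 < 3. Against B1 a score up to 2 is positive, so the proportion is Φ((2.5 − m)/0.7). Against B2 only a score up to 1 is positive, so it is Φ((1.5 − m)/0.7).

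| m | Against B1 | Against B2 |
|---|---|---|
| 0.75 | Φ(2.50) = 99% | Φ(1.07) = 86% |
| 1.5 | Φ(1.43) = 92% | Φ(0) = 50% |
| 2.0 | Φ(0.71) = 76% | Φ(−0.71) = 24% |
| 2.5 | Φ(0) = 50% | Φ(−1.43) = 8% |

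With B1 = 2.5, both columns equal the right-hand one.

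**Step 5: the combined summary of bile acid change.** Let f be the prior-active share of the pool. If every patient has the same true reduction from the pre-drug level and it is fully sustained, prior-active patients contribute about zero change from Baseline 2, and the pooled change is (1 − f) × the true reduction. The protocol plans about 60 + 60 patients but does not give the 005 allocation. Assuming 20, 40 or 50 prior-active patients out of 120, the pool shows 1 − 20/120 = 83%, 1 − 40/120 = 67% or 1 − 50/120 = 58% of the true reduction. For an assumed 110 µmol/L and 40 prior-active patients: (40 × 0 + 80 × −110)/120 = −73 µmol/L. BRIC patients leave this pool, so f would be somewhat larger for the same counts.

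**The case against.** A reader might infer that the endpoint cannot show a sustained effect at all. The documents do not support that. The ≤1 part needs no baseline, so a child who went from 3 to 1 and stays there is 100% positive either way. The placebo-to-120 subgroup has a drug-free baseline. The extreme contrast of 0% against 100% needs a pre-A4250 average of at least 3 and every later score exactly 2; at an average of 2.9, a score of 2 is negative under both baselines.

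Nor does the pooled display govern the results. Section 11.2.2.1 presents Cohort 1 by 005 arm and separately combines placebo-to-120 with Cohort 2 excluding BRIC, which is a drug-free-baseline pool. Section 11.1 disclaims formal hypothesis testing. For bile acids, the Baseline 1 test and the suggested cross-study plot largely answer the point outside the combined display.

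Section 9.1.3 cuts both ways. If it means before 005, exploratory scratching-severity changes already have a pre-drug reference, and the default in section 11.2.2.1 allows exceptions. If it means Baseline 2, near-zero change by visit would itself indicate maintenance. These arguments limit the point. They do not supply a pre-A4250 version of the responder endpoint, and the ambiguity remains: section 9.1.3 also lists the patient-reported version of the same rule, so one child's two responder endpoints could use different baselines.

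It is also tempting to fault the exploratory comparison of 120 µg/kg/day "during the first 24 weeks of Study 008 vs placebo patients over the 24-week treatment period from Study 005 will be carried out" for mixing baselines. The text states no population or pairing rule for it, and that detail may properly sit in the SAP. The SAP is not shown and may also add a Baseline 1 pruritus analysis.

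**Conclusion.** The point holds in a bounded form. For Cohort 1 patients treated with A4250 in 005, the drop part of the pruritus rule is anchored to on-treatment scores and classes sustained partial responses as negative. It affects patients whose pre-A4250 AM or PM average was at least 3 and whose response stopped short of 1. In the illustration the loss ranges from 13 percentage points (99% against 86%, mean 0.75) to 52 (76% against 24%, mean 2.0). It is zero where the pre-A4250 average was below 3.

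Those sizes rest on the assumed SD and stable scores. The distribution of pre-A4250 scores is not in the protocol, so the number of children affected is unknown. The bile acid dilution rests on an assumed allocation and a common effect, and concerns only the combined display. The error runs against the drug, and the by-arm displays make it partly visible. Replacing the primary baseline outright is debatable and not required. Leaving a maintenance objective without any pre-A4250 responder analysis for pruritus, when one is named for bile acids, is a gap worth closing.

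**What to change.** 1. In section 11.2.2.5, for Cohort 1 patients who received A4250 in 005, add the proportion of positive pruritus assessments judged against the 14-day AM and PM averages before the first 005 dose. Report it beside the Baseline 2 version.
2. In the combined Cohort 1 plus Cohort 2 (excluding BRIC) display, use each patient's last pre-A4250 baseline for both pruritus and serum bile acids: the pre-005 baseline for prior-active patients, and the current baseline for ex-placebo and Cohort 2 patients.
3. Reconcile the baseline sentence in section 9.1.3 with the Baseline 2 default in section 11.2.2.1, saying which study's first dose is meant. Carry the result into the synopsis; both country versions shown define the pruritus baseline the same way.

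The cost is wording plus one derivation. It assumes that 005 holds pre-dose diary scores; the plan already draws on 005 pruritus data for the placebo comparison. The downside is that for prior-active patients who completed 005 the change spans both studies, 24 + 72 = 96 weeks, and displays should say so.

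### The one test named for bile acids compares Week 70/72 with the value before Study 005, so it cannot show that the effect was sustained

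*Protocol*

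**What the plan says.** Protocol section 6.1 gives Cohort 1 this primary objective: "To demonstrate a sustained effect of A4250 on serum bile acids and pruritus in children with PFIC Types 1 and 2". For Cohort 2 the verb is only to evaluate.

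Section 11.2.2.1 defines two baselines. For the first, "Baseline 1 will be defined as the last value prior to treatment start in Study A4250-005 for Cohort 1 patients". The second is the last value before treatment in Study 008, and "Baseline 2 will be used in all analyses unless otherwise specified".

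Section 11.2.2.5 then sets a specific rule for bile acids in Cohort 1: the baseline is the mean of two values, one taken pre-dose at Visit 1 of Study 008 and one at Visit 8 of Study 005. For patients given A4250 in Study 005 this is an on-treatment, end-of-005 baseline. At the other end, "The end value is the average of the values at Weeks 70 and 72 in study A4250-008". On method, "The change from baseline over the Treatment Period in serum bile acids will be analyzed mainly by using descriptive statistics". After that comes the one named test: "In addition, change from baseline 1 to end of treatment will be analyzed by using one-sample T-test or Wilcoxon signed-rank test as appropriate". The sentence gives no group, null value, alpha or sidedness.

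On subgroups, section 11.2.2.1 says: "Within Cohort 1, the following subgroups will be presented". They are 40 to 120, 120 to 120, the two combined, and placebo to 120. They are introduced as a layout for descriptive statistics. Section 11.1 says that the study has no formal hypothesis testing.

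**The concern.** A sustained effect means that what was gained by the end of Study 005 was still there at Week 72 of Study 008. The contrast that speaks to this is the change from the end-of-005 baseline in patients already on A4250. The plan leaves that contrast descriptive and puts its test on the change from before Study 005, where the gain made during Study 005 is already counted in the result.

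There is a second difficulty. Baseline 1 is defined for Cohort 1 patients without exception, and Cohort 1 includes patients who were on placebo in Study 005. Their fall from Baseline 1 is a first response to the drug and carries no information on durability.

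At stake is the wording of the conclusion. A small p-value reported beside an objective that uses the word *demonstrate* can be taken as evidence of durability when it shows only that some reduction is present.

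**Working it through.** **The plan's own figures.** None attaches to this test. The only power figure, in section 11.1, concerns the proportion with a surgical event or death: 89% to 96% for n = 48 to 60, true 10% against 30%. Requiring the exact (Clopper-Pearson) upper 95% limit to lie below 30% allows at most 7 events of 48 or 10 of 60. With a true rate of 10% that has probability 89.8% and 96.6%, so the figure is reproduced. It says nothing about bile acids.

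**What the test can tell apart.** For a patient treated since Study 005, let B1 be the value before Study 005, B2 the end-of-005 baseline and W the Week 70/72 mean. Then

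W − B1 = (W − B2) − (B1 − B2).

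The last bracket is the gain in Study 005; call its mean E. The first is the loss since. If a fraction r of the gain is kept, the mean of W − B1 is −rE. A zero null is r = 0, and every r above 0 belongs to the alternative. Sustained means r near 1, that is, W − B2 near zero, and this is not tested.

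**Size, in patients treated since Study 005 only.** Assumptions, none of them in the protocol: normal changes with SD 1, full effect E in SD units, a two-sided 5% t-test, and 40 such patients (two thirds of about 60). The noncentrality is rE√40 and the critical value is 2.02. Example: E = 1 with half kept gives 0.5 × √40 = 3.16, and a rejection probability of 87%. Probability of rejecting in the direction of benefit:

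| Effect kept | E = 0.6 | 0.8 | 1.0 | 1.2 |
|---|---|---|---|---|
| all | 96% | >99% | >99% | >99% |
| half | 46% | 69% | 87% | 96% |
| none | 2.5% | 2.5% | 2.5% | 2.5% |

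With only 30% kept, the probability is still 46% at E = 1 and 79% at E = 1.5.

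**Size, if placebo switchers are pooled in.** Simulation with 40 treated since Study 005 and 20 switchers, the switchers assumed to have the full effect at Week 72:

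| Effect kept by 005-treated patients | E = 0.6 | 0.8 | 1.0 | 1.2 |
|---|---|---|---|---|
| half | 86% | 98% | >99% | >99% |
| none | 31% | 48% | 64% | 79% |

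With 32 and 16 patients the bottom row is 25%, 39%, 54% and 67%. The switcher share is not in the protocol and matters a good deal: at E = 1 and n = 60, rejection after complete loss is 42%, 65% and 81% for shares of 25%, one third and 40%. Over n = 48 to 60, those shares and E = 0.5 to 1.5, the range is 12% to 99%. The Wilcoxon test gives similar rates.

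**The case against.** The strongest reply is that the plan never asks this test to decide anything. Section 11.1 disclaims formal testing, the test enters as an addition to a descriptive analysis, and no success rule hangs on its p-value. The planned bile acid change already starts from the end-of-005 baseline and is shown by Study 005 arm, with a plot across both studies, so waning in patients treated since Study 005 would appear there as a rise, apart from the switchers. This stands and limits the weight of the point. It does not remove it: the descriptive tables have no stated interval or yardstick for *sustained*, and the only named test sits on the other contrast.

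It can also be said that an effect still present against the pre-treatment value is one fair meaning of *sustained*. That is arguable. On that meaning the test is valid in patients treated since Study 005, where complete loss is rejected at the nominal 2.5%, but it remains silent on partial loss.

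A reader might go further and infer that the plan does pool the placebo switchers, so that its test will find an effect even when the treated patients have lost all of it. The documents do not establish that. Whole Cohort 1 is the natural reading, but no group is named, the separate subgroups are already defined, and an analysis plan not shown here may run the test by subgroup. The complete-loss figures also need switchers to keep everything while the others lose everything on the same drug.

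Finally, this is the only named bile acid test, not necessarily the only inference: section 11.2.2.5 also plans an exploratory comparison of the first 24 weeks of Study 008 with Study 005 placebo, method unnamed. It cannot address 72 weeks.

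**Conclusion.** The point holds in this form. The Baseline 1 test does not address the sustained-effect objective, because with a zero null it rejects whenever enough of the reduction remains, including after substantial waning. That needs no pooling: in 40 patients treated since Study 005, rejection after half the effect is lost is 46% to 96% for assumed effects of 0.6 to 1.2 SD. If switchers are pooled, rejection can also exceed the nominal rate after complete loss, by an amount that depends on the assumed switcher share, their assumed full effect and E.

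All these rates are illustrations. Effect size, SD, normality, the two-thirds split and the zero null are assumptions. The point is worth correcting but moderate in weight, since the test carries no formal decision and the by-arm summaries would show a marked loss.

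**What to change.** In Protocol section 11.2.2.5:

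1. State that the Baseline 1 test is run in patients who received A4250 in Study 005 (the combined subgroup already defined in section 11.2.2.1), and report placebo switchers separately, from their last baseline before A4250.
2. For patients treated in Study 005, add a two-sided 95% confidence interval to the planned change from the end-of-005 baseline (mean of Study 005 Visit 8 and Study 008 Visit 1) to Weeks 70/72. Show it beside the reduction from Baseline 1 to that baseline. Present 120-to-120 separately from 40-to-120: the latter changes dose at entry to Study 008, and any added effect of the change could mask waning.
3. Base any statement that the effect was sustained on that interval, read against the reduction reached in Study 005, and not on the Baseline 1 p-value.

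The cost is a few sentences and one table from data already collected. The Baseline 1 test then uses about 40 patients where the pooled reading has 60; at that size its power for a fully kept effect is about 96% or more for E of at least 0.6 SD. The intervals in the two dose subgroups will be wider than in the combined group.
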